 - Patients with ≤PR at completion of 4 cycles, will stop therapy and be taken off protocol at completion of 4 cycles.

- For patients achieving >PR at end of 4 cycles, patients will continue to receive combination therapy with maximum up to 12 cycles.
 - Patients obtaining CR/sCR at any point during cycles in serum and urine will undergo MRD testing using multi-parametric flow cytometry.
 - Patients who attain minimal residual disease (MRD) negative status will stop treatment after 2 additional cycles (maximum 12 cycles).
 - Patients who are MRD positive will stop treatment at completion of 12 cycles. Patients converting from MRD positive status to negative status on subsequent MRD testing can stop after 2 additional cycles
 - Patients achieving <CR/sCR (and >PR at end of 4 cycles) will stop treatment at completion of 12 cycles.
- Upon completion of protocol therapy, patients will be encouraged to proceed onto maintenance therapy or high dose therapy with stem cell rescue under a separate treatment protocol or standard of care. If clinically indicated, patients may need alternative therapy.
- After completion of protocol therapy, patients will remain on study for an additional 3 years for survival analysis.

[figure not shown]
Treatment Plan (see schema below)

- Cycle 1 ONLY: Carfilzomib 20 mg/m² per dose, days 1 and 2; Carfilzomib 45 or 56 mg/m² per dose, days 8, 9, 15, and 16
- Cycles 2- up to 12: Carfilzomib 45 or 56 mg/m² per dose, days 1, 2, 8, 9, 15, and 16
- Cycles 1- up to 12: Lenalidomide 25 mg/day, days 1–21 every 28 days
- Cycles 1-4: Dexamethasone 20 mg/dose, days 1, 2, 8, 9, 15, 16, 22, and 23
- Cycles 5- up to 12: Dexamethasone 10 mg/dose, days 1, 2, 8, 9, 15, 16, 22 and 23
- After receiving first 4 cycles, patients who are considered to be eligible for subsequent high dose therapy/autologous stem cell transplant (ASCT) will undergo autologous stem cell harvesting for potential use in the future. For patients who choose to undergo stem cell harvest, next cycle may be delayed for up to 7 weeks.
- If patients achieve > PR after completion 4 cycles, patients may receive additional combination therapy (maximum permissible 12 cycles). Patients may go onto receiving additional maintenance phase therapy with lenalidomide under a separate treatment protocol.
 - Patients obtaining CR/sCR and MRD negative status by flow cytometry will stop treatment after 2 additional cycles (maximum 12 cycles) delivered.

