6.1 Subject Inclusion Criteria

- Newly diagnosed patients with histologically confirmed MM based on the following criteria:
 - Clonal plasma cells in the bone marrow
 - Measurable disease within the past 4 weeks defined by any one of the following:
 - Serum monoclonal protein ≥ 1.0 g/dL
 - Urine monoclonal protein >200 mg/24 hour
 - Involved serum immunoglobulin free light chain > 10 mg/dL AND abnormal kappa/lambda ratio
- Evidence of underlying end organ damage and/or myeloma defining event attributed to underlying plasma cell proliferative disorder meeting at least one of the following:
 - Hypercalcemia: serum calcium >0.25 mmol/L (> 1 mg/dL) above upper limit of normal or ≥ 2.75 mmol/L (11 mg/dL)
 - Anemia: hemoglobin value <10 g/dL or > 2 g/dL below lower limit of normal
 - Bone disease: ≥ 1 lytic lesions on skeletal X-ray, CT, or PET-CT. For patients with 1 lytic lesion, bone marrow should demonstrate $\geq 10\%$ clonal plasma cells
 - Clonal bone marrow plasma cell percentage $\geq 60\%$
 - Involved/un-involved serum free light chain ratio ≥ 100 and involved free light chain >100 mg/L.
 - > 1 focal lesion on magnetic resonance imaging study (lesion must be >5 mm) in size
- Creatinine Clearance ≥ 60 ml/min. CrCl can be measured or estimated using Cockcroft-Gault method
- Age ≥ 18 years at the time of signing the informed consent documentation

- Eastern Cooperative Oncology Group (ECOG) performance status 0-2
- Absolute neutrophil count (ANC) \geq 1.0 K/uL, hemoglobin \geq 8 g/dL, and platelet count \geq 75 K/uL, unless if cytopenias are deemed to be due disease at discretion of clinical investigator. Transfusions and growth factors are permissible.
- Adequate hepatic function, with bilirubin $<$ 1.5 x the ULN, and AST and ALT $<$ 3.0 x ULN.
- All study participants must be able to tolerate one of the following thromboprophylactic strategies: aspirin, low molecular weight heparin or warfarin (coumadin) or alternative anti-coagulant.
- All study participants must be registered into the mandatory eREMS® program, and be willing and able to comply with the requirements of REMS®.

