For patients undergoing MRD or end of study assessment, the first pulled bone marrow sample will be sent for multi-parametric flow cytometry as a priority. Flow cytometry based assay to rule out MRD (defined as less than 20 abnormal plasma cells) in bone marrow aspirates of CR/sCR patients. For patients with samples demonstrating between 10-20 abnormal plasma cells, cases will be reviewed with hematopathologist and clinical investigator on a case by case basis to determine whether sample is considered MRD positive. Patients with <CR/sCR are considered MRD positive. We will use the MSKCC flow cytometry MRD method which is based on 10-colors in a single tube.¹⁶ The test demonstrates highly similar results when compared to the current Euroflow approach. This test is validated and already in clinical use at MSK. Immunophenotyping of aberrant plasma cells by flow cytometry currently involves, but is not limited to, the use of the following reagents: CD138, CD19, CD45, CD38, and CD56. Characteristic changes in immunophenotypically abnormal plasma cells (CD38 bright and/or CD138 positive) include but are not limited to decreased or absent CD19 and CD45, decreased CD38, increased CD56, decreased CD27, decreased CD81, increased CD117. For patients with non-evaluable samples at MRD assessment, patients can opt for repeat MRD assessment or continue to receive a total of 12 cycles of CRd. For those patients that are MRD negative by flow cytometry during their routine pre-stem cell collection bone marrow assessments,

the result will count towards their MRD evaluation.

Traditional Response Criteria from International Myeloma Working Group Criteria for Multiple Myeloma²²

Evaluation of Response Criteria

- a) Stringent Complete Response (sCR)
 - o Complete Response as defined below plus: Normal FLC ratio and absence of clonal cells in bone marrow by immunohistochemistry or immunofluorescence (presence/absence of clonal cells is based on the kappa/ lambda ratio).
- b) Complete Response (CR)
 - o Negative immunofixation on the serum and urine and disappearance of any soft tissue plasmacytomas and <= 5% plasma cells in bone marrow
- c) Very Good Partial Response (VGPR)

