 - o Serum and urine M-protein detectable by immunofixation but not on electrophoresis or 90% or greater reduction in serum M-protein plus urine M- protein level <100mg per 24h. If the serum and urine M-protein are unmeasurable, a \geq 90% decrease in the difference between involved and uninvolved FLC levels is required in place of the M- protein criteria.
- d) Partial Response (PR)
 - o \geq 50% reduction in M protein and reduction in 24-h urinary M-protein by \geq 90% or to < 200 mg per 24h . If the serum and urine M-protein are unmeasurable, a \geq 90% difference between involved and uninvolved FLC levels is required in place of the M- protein criteria
- e) Stable Disease (SD)
 - o Not meeting criteria for CR, VGPR, PR or progressive disease. All categories also require no known evidence of progressive or new bone lesions if radiographic studies were performed. Radiographic studies are not required to satisfy these response requirements.
- f) Progressive disease (PD)
 - o Requires any one or more of the following:
 - Increase of \geq 25% of nadir in:
 - Serum M-component and/or (absolute increase must be \geq 0.5 g/dl. The serum M-component increases of \geq 1gm/dl are sufficient to define relapse if starting M-component is \geq 5 gm/dl.
 - Urine M-component and/or (the absolute increase must be \geq 200 mg/24h
 - Only in patients without measureable serum and urine M-protein levels: the difference between involved and uninvolved FLC levels. The absolute increase must be >10 mg/dl.
 - Bone marrow plasma cell percentage: the absolute % must be \geq 10%
 - Definite development of new bone lesions or soft tissue plasmacytomas or definite increase in size of existing bone lesions or soft tissue plasmacytomas
 - Development of that can be attributed solely to the plasma cell proliferative disorder

g) Relapse from CR

- Any one or more of the following:
 - Reappearance of serum or urine M-protein by immunofixation or electrophoresis. (Appearance of monoclonal or oligoclonal bands that are different from original isotype may not be defined as "relapse from CR". Often times, such bands may indicate fluctuations in immunological parameters that are not reflective of MM disease. In these situations, immunofixation and electrophoresis will be interpreted by the clinician before being labeled as "relapse"^{23,24}.)
 - Development of $\geq 5\%$ plasma cells in the bone marrow

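### Section 12.0 gives CR no free-light-chain criterion, so a patient eligible on FLC alone can be CR while failing VGPR; the CR rate and the gate to the primary endpoint can be biased upward, to a limited and unknown extent

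*Combined protocol and SAP*

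**What the plan says.** **Entry (6.1).** Any one of three measurability routes is enough. One is "Involved serum immunoglobulin free light chain > 10 mg/dL AND abnormal kappa/lambda ratio".

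**Response categories (12.0, Evaluation of Response Criteria).**
- sCR, item (a): "Complete Response as defined below plus: Normal FLC ratio and absence of clonal cells in bone marrow".
- CR, item (b): "Negative immunofixation on the serum and urine and disappearance of any soft tissue plasmacytomas and <= 5% plasma cells in bone marrow". There is no FLC term.
- VGPR, item (c): where serum and urine M-protein are unmeasurable, a 90% or greater "decrease in the difference between involved and uninvolved FLC levels is required in place of the M- protein criteria".
- PR, item (d): also has an FLC substitute for these patients, likewise printed at 90%.
- PD, item (f): includes a criterion for "Only in patients without measureable serum and urine M-protein levels: the difference between involved and uninvolved FLC levels".
- Relapse from CR, item (g): lists no FLC criterion.

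**General FLC rules (12.0, Disease Parameters).** Item (b) says the FLC assay should inform response when it is the primary determinant and baseline involved FLC is at least 10 mg/dL with an abnormal ratio. Item (d) requires two consecutive determinations. Neither gives an FLC level or ratio for CR.

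**Use of the CR call.** Section 14.0 defines the primary endpoint as CR/sCR with MRD negativity by flow, and counts anyone below CR/sCR as MRD positive. Section 1.0 says: "Patients obtaining CR/sCR at any point during cycles in serum and urine will undergo MRD testing using multi-parametric flow cytometry". MRD negativity then determines when treatment stops (1.0, 3.2, 4.2).

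**The concern.** For a patient followed by FLC, every lower category and progression refer to the marker that measures the disease. CR does not. If serum and urine immunofixation are already negative at entry, the immunofixation part of CR can be met without any change in that marker. The normal-ratio condition under sCR does not close the gap, because the endpoint pools CR with sCR.

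The scale then loses its order, since a higher category can be reached by a patient who fails a lower one. At stake are the secondary CR rate, which uses this definition directly, and entry to the primary endpoint, which rests on 25 patients with cut-offs of 3 versus 4 of 14 and 7 versus 8 of 25. One classification can decide the result at either boundary.

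**Working it through.** **1. The definitions applied to one patient.** Take a hypothetical FLC-only patient with negative serum and urine immunofixation, no plasmacytoma, a 60% fall in the involved-minus-uninvolved FLC difference, a ratio still abnormal, and 4% marrow plasma cells.

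| Category | Test that applies | Result |
|---|---|---|
| PR | FLC limb, printed at 90% | not met (60%) |
| VGPR | FLC difference down by at least 90% | not met (60%) |
| CR | immunofixation negative, no plasmacytoma, marrow plasma cells at most 5% | met |
| sCR | CR plus normal ratio and no clonal cells | not met |

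The patient is CR and fails VGPR. Whether the patient also reaches the primary endpoint depends on flow, which the example leaves open.

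**2. The plan's design reproduced.** Inputs from 14.0: 14 patients in stage 1, stop at 3 or fewer, 25 in total, success at 8 or more, p0 = 0.20, p1 = 0.45. Let X be stage 1 successes, Binomial(14, p), and Y stage 2 successes, Binomial(11, p).

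- Early termination at 20%: P(X ≤ 3) = 0.0440 + 0.1539 + 0.2501 + 0.2501 = 0.698 (plan: 70%).
- Success at 20%: sum over X ≥ 4 of P(X)·P(Y ≥ 8 − X) = 0.1720·0.1611 + 0.0860·0.3826 + 0.0322·0.6779 + 0.0092·0.9141 + 0.0024·1 = 0.093 (limit 0.10).
- Success at 45%, same formula: 0.903 (required 0.90).

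The design is correct as stated.

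**3. Illustration of size.** The number of exposed patients is not in the documents, so one and two of 25 are assumptions. All other patients are at 20%. The exposed patient is counted a success with probability r and is equally likely to hold any of the 25 places.

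*One patient, r = 100%.* If in stage 1 (weight 14/25 = 0.56) the success probability is 0.1732. If in stage 2 (weight 0.44) it is 0.1495. Average: 0.56·0.1732 + 0.44·0.1495 = 0.163. With one patient the result is linear in r from the 20% base: 0.0933 + (r − 0.20)/0.80 × (0.1628 − 0.0933). This gives 0.102 at r = 30% and 0.119 at r = 50%.

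*Two patients, r = 100%.* Weights: both in stage 1, 182/600 = 0.3033; one in each, 308/600 = 0.5133; both in stage 2, 110/600 = 0.1833. Average: 0.3033·0.2941 + 0.5133·0.2667 + 0.1833·0.2153 = 0.266. The same calculation gives 0.111 at r = 30% and 0.150 at r = 50%.

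| Exposed patients | r = 30% | r = 50% | r = 100% |
|---|---|---|---|
| 0 | 0.093 | 0.093 | 0.093 |
| 1 | 0.102 | 0.119 | 0.163 |
| 2 | 0.111 | 0.150 | 0.266 |

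**4. Secondary CR rate.** Flow plays no part here. Each patient called CR on this reading adds 1/25 = 4 percentage points in a group of 25.

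**The case against.** The strongest reply is that the gate is not the endpoint. CR still requires at most 5% marrow plasma cells and no plasmacytoma, and the primary endpoint adds flow MRD negativity, defined in 12.0 as fewer than 20 abnormal plasma cells. A patient with real residual disease in the marrow should fail there. This stands, and it makes the 100% column an upper case.

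Second, the exposed group is narrower than all FLC-only patients. Measurability in 6.1 is at least 1.0 g/dL in serum or more than 200 mg/24 h in urine. A patient below both can still be immunofixation-positive, and for that patient CR does demand a change. This stands too; the group may be empty.

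Third, the plan is not silent on FLC. Section 1.0 lists FLC among the monthly response tests, Disease Parameters (b) and (d) direct its use and confirmation, and 3.2 calls for marrow confirmation of CR by standard criteria. An assessor could withhold CR on that basis. But none of this text sets an FLC condition for CR, so the call is left to judgement in a single-arm trial. Whether the cited response criteria fill the gap cannot be judged from these documents.

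Fourth, Disease Parameters (b) warns that FLC varies with renal function. Entry requires creatinine clearance of at least 60 ml/min, which weakens that as a reason for leaving FLC out.

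**Conclusion.** The inconsistency within 12.0 is real and can be verified by reading it. For immunofixation-negative, FLC-only patients the CR definition can misclassify, so the CR rate and the CR/sCR gate can be biased upward. It should be corrected, but it does not undermine the design: sample size, cut-offs and error rates are right.

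The size is unquantified. The range of 0.10 to 0.27 for one or two patients rests on assumed numbers and on an assumed counted rate of 30% to 100%; with no exposed patients there is no effect.

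Two stronger readings are not supported. A reader might infer that CR does not test the disease in these patients, or that the MRD-negative rate is necessarily inflated; the marrow, plasmacytoma and flow requirements rule out the first and leave the second only possible. A reader might also treat one or two extra successes as raising the rate for all 25 patients to 24% or 28%, which gives 0.204 and 0.355. That overstates the effect, because only the exposed patients' results change; even counted as certain successes they give 0.163 and 0.266.

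**What to change.** Reconcile Disease Parameters (b) and (d) in 12.0 with the response categories so that, for endpoint classification, CR in patients whose only measurable disease is serum FLC carries an explicit FLC criterion at least as strict as the VGPR limb. The sponsor should choose the criterion; the documents place a normal ratio only under sCR and do not settle what CR should require. State at the same time whether relapse from CR has a matching FLC criterion.

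The FLC results are already collected on Day 1 of each cycle (9.5.1), and the existing two-determination rule covers confirmation, so no new test is needed. The cost is a short clarification in 12.0. The downside is that CR may be called slightly later, or less often, in this subgroup.

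Sections 1.0, 3.2 and 4.2 use the same CR call to trigger MRD testing and, through it, the end of treatment, and they word it differently: 1.0 and 4.2 refer to serum and urine, 3.2 to serum and/or urine. The sponsor should reconcile these with the clarified definition. That part is clinical management, and no rule is proposed here.

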12.0 CRITERIA FOR THERAPEUTIC RESPONSE/OUTCOME ASSESSMENT

Disease Parameters

- a) A "measurable" serum M-protein is ≥ 1 g/dL or a "measurable" urine M-spike is ≥ 200 mg/24 hours or "measurable light chains" are either a serum kappa or lambda FREE light chain of ≥ 10 mg/dL along with an abnormal kappa to lambda free light chain ratio, patient is considered to have "measurable" disease.
- b) The serum free light chain (FLC) assay is of particular use in monitoring response to therapy in patients who have light-chain disease. When using this assay, it is important to note that the FLC levels vary considerably with changes in renal function and do not solely represent monoclonal elevations. Thus both the level of the involved and the uninvolved FLC isotype (i.e., the involved/uninvolved ratio or involved-uninvolved difference) should be considered in assessing response. The serum FLC assay should be used in assessing response if the baseline level of the involved FLC is ≥ 10 mg/dL and abnormal kappa/lambda ratio (when primary determinant of response).
- c) For patients with initial baseline 24-hr UPEP samples demonstrating ≥ 100 mg/24 hrs, patients with continue to have 24-hr UPEP samples day 1 of each cycle. Once 24-hr UPEP is <100 mg/24 hrs, patient can have random UPEP with IFE until achieving negativity. If initial baseline 24-hr UPEP sample is IFE positive and/or <100 mg/24, patients can have random UPEP samples with IFE until achieving negativity. Once random UPEP and IFE is negative, no further urine samples are needed (unless primary determinant of response)
- d) In order to be classified as a response, confirmation of serum monoclonal protein, serum immunoglobulin free light chain (when primary determinant of response) and urine monoclonal protein (when primary determinant of response) results must be made by verification on two consecutive determinations at different timepoints.
- e) Compression fracture does not exclude continued response and may not indicate progression; findings of worsening compression fracture will be subject to interpretation of the clinical investigator.

Minimal Residual Disease

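### For patients followed by free light chains alone, the partial response criterion repeats the 90% threshold of very good partial response and does not state a decrease, so it cannot be applied as printed

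*Combined protocol and SAP*

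**What the plan says.** Section 12.0 lists the response categories under the heading "Traditional Response Criteria from International Myeloma Working Group Criteria for Multiple Myeloma".

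- **VGPR, M-protein limb:** one route is "90% or greater reduction in serum M-protein plus urine M- protein level <100mg per 24h".
- **VGPR, FLC limb:** when serum and urine M-protein are unmeasurable, at least a "90% decrease in the difference between involved and uninvolved FLC levels is required".
- **PR, M-protein limb:** at least a "50% reduction in M protein and reduction in 24-h urinary M-protein by" 90% or more, or to below 200 mg/24 h.
- **PR, FLC limb:** on the same trigger, at least a "90% difference between involved and uninvolved FLC levels is required in place of the M- protein criteria".
- **Stable disease:** the residual category, "Not meeting criteria for CR, VGPR, PR or progressive disease".

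The FLC limb can come into use. Section 6.1 accepts any one of three measures of disease, and one of them is "Involved serum immunoglobulin free light chain > 10 mg/dL AND abnormal kappa/lambda ratio". Section 12.0, Disease Parameters (b), says "The serum FLC assay should be used in assessing response if the baseline level of the involved FLC is" at least 10 mg/dL with an abnormal ratio, when FLC is the main determinant of response.

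Section 2.0 defines overall response as PR or better. Section 14.0 estimates ORR under International Myeloma Working Group (IMWG) criteria, at each cycle and as best response, with exact 95% confidence intervals. Section 1.0 refers the reader to Section 12.0 for the response definitions.

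**The concern.** PR and VGPR are meant to be successive grades. The serum limbs grade them (50% against 90%), and the urine limbs still do so by level (below 200 against below 100 mg/24 h). The FLC limbs show the same number for both, and no other place in the document gives a different FLC value for PR. The PR sentence also lacks the words that make the VGPR sentence a change from baseline.

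At stake is how FLC-only patients are counted in ORR. An assessor who follows the printed text and one who follows some other PR cut-off would report different response rates from the same laboratory data. The per-cycle ORR is the more exposed. On the parallel reading, an FLC-only patient counts as a non-responder until the fall reaches 90%, while a serum patient counts from 50% once the urine limb is met.

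**Working it through.** The plan gives no figure of its own to reproduce here, so the check is logical, followed by the effect on ORR.

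**Step 1. Parallel reading (PR taken as a decrease in the FLC difference).** Take a patient with unmeasurable serum and urine M-protein who is not in CR/sCR and has not progressed.

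| Fall in FLC difference | Meets VGPR (≥90%)? | Meets PR (≥90%)? | Category |
|---|---|---|---|
| 95% | yes | yes | VGPR |
| 90% | yes | yes | VGPR |
| 89% | no | no | stable disease |
| 75% | no | no | stable disease |
| 50% | no | no | stable disease |

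No value of the fall gives PR as the final category.

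**Step 2. Same relative fall, two categories (illustrative values).**
- Serum M-protein 3.0 to 1.0 g/dL: (3.0 − 1.0)/3.0 = 66.7%. With the urine limb met, this is PR.
- Involved FLC 31 to 11 mg/dL with uninvolved 1 mg/dL, so the difference goes from 30 to 10: (30 − 10)/30 = 66.7%. This is stable disease.

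**Step 3. Literal reading (a 90% difference between the two chains, with no baseline).** For the same patient:
- Before treatment: (31 − 1)/31 = 96.8%.
- After the fall: (11 − 1)/11 = 90.9%.

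The line is met before any drug is given, so on this reading it does not measure response at all.

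**Step 4. Effect on ORR.** Section 14.0 gives 25 patients at the end of phase II and a projected maximum of 37 for the study. One patient moves ORR by 1/25 = 4.0 points or 1/37 = 2.7 points. The exact (Clopper-Pearson) limits below assume, for illustration, that everyone else responds.

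| Responders | ORR | Exact 95% CI |
|---|---|---|
| 25/25 | 100% | 86.3% to 100% |
| 24/25 | 96.0% | 79.6% to 99.9% |
| 37/37 | 100% | 90.5% to 100% |
| 36/37 | 97.3% | 85.8% to 99.9% |

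Best-response ORR changes only for a patient whose fall never reaches 90%. Per-cycle ORR also changes at every assessment before 90% is reached.

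**Step 5. What does not move.**
- Anything below CR/sCR already counts as MRD positive, so the primary endpoint and the Simon stopping rule are unaffected.
- VGPR-or-better and CR do not use the PR line.
- The cycle-4 rule treats PR and stable disease alike, since both fall in PR or less.

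**The case against.** The strongest reply is that Sections 12.0 and 14.0 both name the IMWG criteria, so experienced assessors may score from that source and the printed slip may never matter. This mitigates the problem but does not settle it. Section 12.0 prints its own definitions, Section 1.0 sends the reader there, and nothing says how a departure from the cited source is to be handled.

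A second reply is that the missing words may have been lost when the text was extracted; the progression list in the same section also seems to have lost some. That is plausible, but dropped words would not explain the repeated 90%.

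Third, the urine limb of PR also uses 90%, so a 90% figure under PR is not odd in itself. That is fair, but the urine limb still separates PR from VGPR by absolute level, and the FLC limb has nothing comparable.

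A reader might infer that ORR will certainly be understated. The documents do not support that. Understatement follows on the parallel reading, the literal reading would overstate ORR, and how a given patient would actually be scored is undetermined. A reader might also set the 4.0 points against the 2% non-response implied by the 98% ORR quoted for the earlier study in Section 3.1. That benchmark is unsafe: the same paragraph gives 42 responders and 45 evaluable patients, and 42/45 = 93.3%. Nor do the documents allow an estimate of how many patients are affected, because they give no expected share of FLC-only patients.

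**Conclusion.** The PR criterion for FLC-only patients is wrong as written. On the workable reading the category is empty and falls below 90% drop out of ORR; on the literal reading it is not a response criterion. Either way it needs correcting.

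The reach is limited: the PR/stable disease split and a descriptive secondary rate that carries no test or decision rule. The cost per affected patient is certain (4.0 points at 25, 2.7 at 37), but the number of such patients is unknown and may be zero. The direction of the error is conditional on the parallel reading. The confidence limits rest on the illustrative assumption that all other patients respond. No correct cut-off is asserted here, because the cited criteria are not reproduced in the document.

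**What to change.** Confine the change to this one line. Reconcile the PR FLC criterion with the VGPR line and with the cited response criteria. Word it as a decrease from baseline in the involved-minus-uninvolved FLC difference, with a threshold that distinguishes PR from VGPR, as the serum limbs already do. Score, or re-score, patients with unmeasurable serum and urine M-protein on the corrected line, and report their number beside ORR.

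A general statement that the cited criteria override the printed text is not advised. It would also reach the CR/sCR definitions behind the MRD endpoint and the protocol's own handling of new bands on immunofixation, with effects that cannot be judged from this document.

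The cost is one line of text and a re-scoring exercise. Section 9.5.1 already collects FLC at baseline and on Day 1 of each cycle, so no new tests or patients are needed.
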